For purposes of comparison to MEG resting state, echo-planar imaging-gradient recalled echo (EPI-GRE) data normally acquired during functional MRI scanning (fMRI) will be acquired during the MRI session. Subjects will simply rest in the prone position with their eyes open for 2 minutes and closed for 2 minutes. The 10 minute baseline MRI scan will allow us to compare the generators of resting state MEG gamma-band to resting state activation in fMRI.

The total MRI procedure, if patients consent to the additional sequences, will last approximately 70 minutes and will begin with the anatomical portion. In case the study subjects feel any discomfort anytime after this first acquisition, they will be freed of terminating the additional scans without being disqualified from the study.

MEG Data Collection: Magnetic field data will be recorded using a whole head neuromagnetometer (4D Neuroimaging) with an array of 248 sensors at rest with eyes open for 2 minutes and closed for 2 minutes at a 678 Hz sampling rate. Data will be processed offline using a 0.1-100 Hz band pass filter. Data will be manually examined and five 6-second artifact free epochs for both eye-open and closed conditions will be selected for further analyses. Artifact correction if needed will be performed using independent components analysis.¹⁰⁸ Sensors will be realigned to a common sensor array to allow group level analysis in a shared brain space.¹⁰⁹

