AIM 3 Rationale and Design: rTMS can improve cognition in PD without dementia⁵², PD with depression⁸⁰, older adults¹²² and in AD¹²³ but has not been tested in PD-MCI. Given the need for improved cognitive treatments and possible differences in rTMS effects on PD-MCI pathophysiology it is important to specifically test rTMS in this population. Prior studies as well as our own pilot data suggest that rTMS modulates cortical connectivity,^{16,17} thus rTMS provides not only a potentially effective intervention but an important causal test of our associative data and theoretical link between cortical connectivity and cognitive dysfunction in PD. Our *clinical objective* for this experiment is to determine whether rTMS improves cognitive outcomes in PD-MCI. Our *mechanistic objective* is to determine whether rTMS normalizes patterns of cortical connectivity. We *hypothesize* that high-frequency bifrontal rTMS will partially normalize patterns of cortical connectivity linked to frontal nodes and will improve cognitive measures. To test this hypothesis 55 PD-MCI subjects will be randomized to a 10-day course of real or sham bifrontal high frequency rTMS. We will measure cognitive and MEG outcomes pre-treatment and on the day of the last treatment (neuropsych testing and MEG procedures may be separated by 1 day if patient is fatigued) and repeat cognitive measures 28 days post rTMS to assess the durability of cognitive changes.

TMS: TMS will be administered using a 70-mm diameter air-cooled figure-of-8 coil and SuperRapid² Magstim Stimulator. We will first define the subject's resting motor threshold (MT) by localizing the hand area of motor cortex and determining the minimal TMS amplitude needed to produce a motor-evoked potential of 50 microV on 4 of 8 trials measured by EMG over the first dorsal interosseous muscle (Biopac, Goleta, CA). Once the MT is determined, repetitive pulses will be delivered to the right and left pre-frontal cortex (Brodmann area 46) using a frameless stereotactic navigation system and the subject's MRI in Brainsight software. Depending on our preliminary results from Aim 1, we may change our target if it is evident that a particular frontal node shows high clustering within beta or theta frequency bands. This type of targeting based on functional data has been previously performed and may enhance TMS effects on intrinsic connectivity.¹⁶ Stimuli will be delivered at 20 Hz at 90% rMT for 25 trains of 30 pulses per train, inter-train

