interval of 30 seconds for a total of 750 pulses per hemisphere, which is well within the most recent international TMS safety guidelines.¹²⁹ This dose and duration of rTMS is based on physiological studies of healthy adults and treatment studies of cognition in PD and Alzheimer’s disease.^{52, 123} Side of first stimulation (left vs right hemisphere) will be counterbalanced across subjects. Sham stimulation will be delivered using a sham coil fitted with electrodes to mimic both the auditory and somatic sensation of real TMS as I have performed in prior TMS trials.¹⁹

Schedule of Procedures

	Baseline Procedures ²	← 2 weeks →			28 days post-rTMS Session 10 ¹
		rTMS Session 1 ¹	rTMS Sessions 2-9 ¹	rTMS Session 10 ¹	
Informed consent	X				
MRI (anatomical and optional functional scans)	X				
MEG	X			X ¹	
Neuropsych tests	X			X ¹	X ¹
rTMS (real or sham) ¹		X ¹	X ¹	X ¹	
Randomization to real or sham TMS ¹	X				

¹PD-MCI subjects only

²Baseline procedures to be completed within 1 week of rTMS Session 1

D. Description, Risks and Justification of Procedures and Data Collection Tools:

PD-MCI and mild dementia patients may be considered a vulnerable population due to cognitive dysfunction but are necessary to answering our research questions. We are cognizant of this issue and will carefully assess potential participant’s understanding of the study, particularly of study activities and risks. If there are any concerns on the part of the investigator or potential participant, we will require that their guardian participate in the consenting process and sign an informed consent. We will also require that PD-MCI subjects give consent, or at minimum assent if fully informed consent is not possible. Our protocol and consent forms will be approved by our local IRB before approaching any potential subjects.

After enrollment and screening assessment, PD and PD-MCI subjects will undergo neuropsychological testing, magnetoencephalography (MEG) recordings, and MRI. PD-MCI subjects will then be randomized in a 1:1 ratio to real or sham TMS groups using MAPLE 9.0 software (Waterloo, Canada). Baseline neuropsychological testing, MEG, and MRI may be performed over multiple days, but all will be completed within 1 week and within 1 week of first TMS session for PD-MCI subjects.

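### Randomisation is scheduled at baseline, up to a week before rTMS Session 1 and apparently before the motor threshold is found, so losses unrelated to arm can fall after allocation

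*Combined protocol and SAP*

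**What the plan says.** - **Number and allocation.** Section IV.C (Aim 3) states that "55 PD-MCI subjects will be randomized to a 10-day course of real or sham" stimulation. Section IV.D puts allocation after neuropsychological testing, MEG and MRI: "PD-MCI subjects will then be randomized in a 1:1 ratio to real or sham TMS groups".
- **Timing.** In the Schedule of Procedures, the row "Randomization to real or sham TMS" has one mark, under Baseline, and none under Session 1. A footnote lets baseline procedures finish up to 1 week before Session 1. Section IV.D says of the baseline tests that "all will be completed within 1 week and within 1 week of first TMS session for PD-MCI subjects". Neither place sets a minimum gap.
- **Motor threshold.** The TMS paragraph of section IV.C begins by defining the "resting motor threshold (MT) by localizing the hand area of motor cortex", and continues: "Once the MT is determined, repetitive pulses will be delivered". The threshold has no row in the schedule and is not among the procedures that section IV.D lists before randomisation.
- **Losses.** Section IV.F (Aim 3) allows 5 drop-outs from 55, leaving 25 per group for the MDRS calculation, without saying when or why they occur. It names no analysis set and gives no rule for patients who are randomised but never treated.

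**The concern.** Allocation best comes as late as practicable, so that patients who will not start treatment drop out of the count before they are randomised. Here the schedule leaves room for two kinds of loss after allocation and before any stimulation: withdrawal between baseline and Session 1, and failure to find a motor threshold. Provided the allocation is not disclosed in the interval, neither can be caused by the arm, because nothing that differs by arm has yet been given. Both could therefore be found before allocation.

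At stake is precision, or dilution of the effect. Excluding such patients shrinks the sample and departs from analysis as randomised; keeping them puts untreated patients in the real-stimulation arm. The plan does not say which it would do.

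**Working it through.** **1. Order of events.**

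| Step | Where the plan puts it |
|---|---|
| Neuropsychological tests, MEG, MRI | Baseline, before randomisation (IV.D; schedule) |
| Randomisation | Baseline column only (schedule) |
| Gap to Session 1 | At most 1 week; no minimum (schedule footnote; IV.D) |
| Motor threshold | First step of TMS, before the pulses (IV.C); no schedule row; order relative to randomisation not stated |
| First stimulation | Session 1 |

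A gap after allocation is permitted by the text. That the threshold falls after allocation is an inference: it opens the TMS procedure and is missing from the pre-randomisation list.

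**2. The plan's own figures (IV.F, Aim 3).** Inputs: difference 10, SD 13, alpha 0.05, 55 randomised, 5 drop-outs.

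- Drop-out step: 5/55 = 9.1%, and 50/(1 − 5/55) = 55. This reproduces.
- Effect size: d = 10/13 = 0.77. This reproduces.
- Power at 25 per arm, two-sided t test: the noncentrality is d × √(n/2) = 0.769 × √12.5 = 2.72 on 48 degrees of freedom, giving 76.0%. The normal approximation gives 77.6%. The stated 80% does not reproduce. Sidedness is not stated; a one-sided test gives 85.0% (t) or 85.9% (normal), which does not match either.
- With all 55 evaluable (27.5 per arm on average): 0.769 × √13.75 = 2.85, giving 80.0%.

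The gap between 80% and 76% is a separate matter. It is relevant here only because it shows that, two-sided, there is no spare power to absorb losses.

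**3. Illustration.** The documents give no figure for losses between randomisation and Session 1. Assume k of the 55 are lost there, spread evenly over the arms, with no other losses.

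- *Excluded:* n per arm = (55 − k)/2, difference 10.
- *Analysed as randomised:* all 55 are followed, and untreated real-arm patients get no benefit. The difference becomes 10 × (1 − k/55), with 27.5 per arm and SD 13.

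| k | n per arm if excluded | Power, excluded | Difference as randomised | Power, as randomised |
|---|---|---|---|---|
| 0 | 27.5 | 80.0% | 10.00 | 80.0% |
| 1 | 27.0 | 79.2% | 9.82 | 78.5% |
| 3 | 26.0 | 77.6% | 9.45 | 75.4% |
| 5 | 25.0 | 76.0% | 9.09 | 72.1% |

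The most that later allocation could recover is 80.0 − 76.0 = 4 points (losses excluded) or 80.0 − 72.1 = about 8 points (analysed as randomised), and only if a number equal to the whole drop-out allowance fell in this gap.

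**The case against.** The case for leaving the plan alone has real content.

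- **The gap may be short.** One week is a maximum. Randomisation follows tests that may themselves spread over several days, so the interval could be a day or less. This stands, and it limits the likely number of losses.
- **The threshold order is inferred.** Nothing forbids finding the threshold before allocation, and nothing suggests that failure to find one is common. This stands too. Equally, nothing requires the threshold first, and the listed sequence points the other way.
- **Losses are expected elsewhere.** TMS contraindications are exclusion criteria (IV.B). Section IV.E names the two weeks of daily treatment as the retention problem and reports 100% retention in an earlier apathy trial. Later randomisation cannot prevent drop-out during treatment.
- **Recruitment has slack.** Section IV.B asks for capacity of up to 150, against 25 + 55 = 80 planned, which leaves 70. That covers losses found before allocation. No rule says that a randomised patient may be replaced.

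A reader might also infer that the baseline MEG should be confirmed usable before allocation, since epochs are selected after recording and "Data will be processed offline using a 0.1-100 Hz band pass filter". One might then take the 5-in-50 allowance of Aims 1 and 2 as a 10% failure rate and expect 5 to 6 of 55 patients to be lost. The documents do not support that step. The 10% is a planning margin, which Aim 1 shares with drop-outs. The 5 drop-outs in Aim 3 belong to the MDRS calculation, and Aim 3 has no MEG sample-size calculation. Above all, a patient with an unusable baseline MEG can still be treated and give a full MDRS change. Turning such patients away would add an eligibility rule that the plan does not contain and would remove them from the primary clinical comparison.

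**Conclusion.** The point holds as a minor, low-cost improvement. As written, the schedule permits allocation up to a week before first treatment and does not place the motor threshold ahead of it. Some losses unrelated to arm can therefore fall after randomisation, in a comparison with no spare power and no stated analysis set.

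The size is unknown and probably small. The illustration runs from about 1 power point (1 loss, excluded) to about 8 (5 losses, analysed as randomised), on a two-sided t test with the plan's 10 points and SD 13. The lower figures assume that untreated real-arm patients gain nothing.

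Two stronger readings go too far. The documents do not show that patients will be lost in this gap, nor that the threshold is definitely found after allocation. They also do not point to a biased comparison: if the allocation stays undisclosed, the harm is to precision or through dilution. Selective exclusion of untreated patients would be a further problem, but the plan does not say it will do that.

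**What to change.** Move the randomisation mark in the Schedule of Procedures from Baseline to rTMS Session 1, and amend the allocation sentence in section IV.D to match. Suggested wording: *Allocation is opened at the Session 1 visit, only after the participant has attended, eligibility has been reconfirmed and the motor threshold has been determined. Participants who do not reach this point are recorded as not randomised.*

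This is one cell and one sentence. It adds no visit and leaves the stimulation settings, outcomes and planned number unchanged. The small downside is practical: the allocation must be available to the person delivering the session at that visit. Patients with an unusable baseline MEG should remain eligible for randomisation, since they can contribute to the MDRS comparison. If the team already determines the threshold before allocating, the amendment simply records that.

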MEG Data Processing: Following data acquisition, there are 4 major steps for graph theory analysis.⁶³ First, data will be transformed into the frequency domain using Morlet wavelets and parceled into six standard frequency bands: delta (1-4 Hz), theta (4-8 Hz), alpha (8-12 Hz), low beta (12-20 Hz), high beta (20-30 Hz) and gamma (30-60 Hz).¹¹⁰ Further analyses will be performed separately for each band. Second, the strength of functional connectivity must be calculated between all sensors. Granger causality will be used for this step, providing a directional weighted measure of connectivity suitable for graph theory.^{111, 112} Third, functional connections between nodes will be used to create a network graph. This is matrix representing the directed weighted connection strengths between all sensors for each frequency band. Advantages of creating a weighted network graph include ensuring full connectedness and avoiding potentially arbitrary thresholds required for binary networks.⁶¹ Finally, graph analyses can be performed on the network graph using the Matlab-based Brain Connectivity Toolbox⁶¹ and custom Matlab code. Our *primary MEG outcome measure* will be network small-worldness, calculated as the ratio of the mean clustering coefficient to the mean path length normalized to a randomly connected network.¹¹³ *Planned secondary MEG outcome measures* will include global efficiency (a measure of global integration related to path length), nodal efficiency (a measure of modularity)⁶⁰, and degree distribution (a measure of network resilience)¹¹⁴.

B. Description of Population to be Enrolled:

We will enroll 25 PD subjects over the age of 40 without cognitive impairment diagnosed with probable PD using UK Brain Bank Criteria³⁸ and 55 PD subjects over the age of 40 with MCI or mild dementia using the Movement Disorder Task Force 2012 criteria and a Clinical Dementia Rating scale score (CDR) less than 2.^{39, 40} All study visits will be performed in subjects' best dopaminergic On state. PD MCI and mild dementia subjects will be tested on anticholinesterase therapy if already taking these medications given the potential difficulty of finding drug naïve subjects; long half-life of these medications; and desire to find measures robust to medication effects as seen in prior MEG studies.⁴¹

Exclusion criteria:

- 1) features suggestive of other neurological disorders
- 2) DBS
- 3) evidence for active depression or Hospital Anxiety Depression Scale⁴² score \geq 11

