in small-worldness or other MEG features. With a total *sample size* of 50 (25 per group allowing for 5 drop-outs from original 55) we will be able to determine a between group difference of 10 points on the MDRS (assuming a SD of 13 as per prior trials and an effect size 0.77)¹²⁴ with 80% power and 0.05 significance. This sample size is comparable to prior PDD studies. For example, a study of rivastigmine in PDD detected significant change on the Mattis with only 28 subjects.¹²⁴

Exploratory Aim Statistical Analyses and Sample Size: We will address our exploratory research questions by looking at Spearman correlations or linear models of MEG and MRI measures. Power considerations are similar as for Aim 1 with detection of correlations of 0.18 or higher between our MEG and MRI features with 80% power 0.05 significance.

G. Summarize Knowledge to be Gained:

PD is the second most common neurodegenerative disease, affecting over one million Americans and dementia is the most common cause of nursing home placement in this population.^{53, 54} Our understanding of the neurobiological mechanisms of cognitive dysfunction in PD are limited and we do not have efficacious treatments. This research will address this significant public health issue in three major ways: 1) Identify abnormalities in cortical connectivity associated with cognitive dysfunction in PD; 2) Develop a MEG biomarker for cognitive dysfunction in PD; and 3) Evaluate the potential for TMS to induce durable changes in PD cognitive function and connectivity. Given the burden of dementia in this population, we feel that the minimal risks involved are justified both to individual PD and PD-MCI subjects, the larger population of PD and PD-MCI patients, and to society as a whole. Recent TMS studies using published safety guidelines suggest that the risks of TMS may be even lower than previously described. Even using conservative estimates and anticipating some discomfort from prolonged sitting and cognitive testing, we argue that this research is imperative to advance this field and ultimately to provide relief to these patients and their caregivers.

H. References:

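### Aim 3 randomises a mix of MCI and mild dementia with no stratification specified and no term for cognitive stage in the analysis; the likely loss is small and the remedy is cheap

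*Combined protocol and SAP*

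**What the plan says.** Section IV.B (population) enrols "55 PD subjects over the age of 40 with MCI or mild dementia using the Movement Disorder Task Force 2012 criteria" and a CDR score below 2, so two cognitive stages are admitted. Section IV.C (Aim 3) then states that "55 PD-MCI subjects will be randomized to a 10-day course of real or sham bifrontal high frequency rTMS", using the MCI label for the same number of patients. Section IV.D opens by referring to both MCI and mild dementia patients, and gives the whole allocation method: "PD-MCI subjects will then be randomized in a 1:1 ratio to real or sham TMS groups using MAPLE 9.0 software". This follows enrolment, screening and baseline neuropsychological testing.

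No section mentions blocks, strata or minimisation, and none says that they will not be used. The only balancing device described concerns the order of hemispheres: "Side of first stimulation (left vs right hemisphere) will be counterbalanced across subjects".

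Section IV.F compares the arms on MDRS change, and on change in small-worldness, by repeated measures ANOVA. No covariate or stage factor is named for Aim 3. Age and motor severity are named for Aim 1 only. Section IV.A offers the UPDRS motor score as a covariate in models that it does not identify; that is motor severity, not cognitive stage. The sample size is "25 per group allowing for 5 drop-outs from original 55".

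**The concern.** Stage is a cognitive classification and the primary outcome is a cognitive scale, so the two are closely tied. Stage is available before allocation, yet the plan uses it neither to balance the arms nor to explain variance in the analysis. In a trial of 55, one arm can receive noticeably more dementia patients by chance. If patients with dementia change differently over two weeks from patients with MCI, part of the observed arm difference would then reflect case mix, and the unmodelled stage effect would sit in the error term. Even if neither effect were large, a visible baseline imbalance weakens the credibility of a small trial that is intended to inform a larger one.

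**Working it through.** **Inputs.** From section IV.F: 10-point difference, SD 13, effect size 0.77, 25 per arm, significance level 0.05 (taken as two-sided), 80% power. From sections IV.B and IV.C: 55 randomised, 1:1. Not in the documents, and therefore assumed with ranges: the dementia share (20% to 50%) and the difference between stages in mean MDRS change (1 to 3 points). The SD of 13 is taken as the SD of the analysed measure; the plan does not say which SD it is.

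**1. The plan's own figure.** Effect size 10/13 = 0.769, which agrees with 0.77. With 25 per arm the noncentrality is 0.769 × √(25/2) = 2.72. A two-sided t-test gives 76.0% power (normal approximation 77.6%), not 80%. That shortfall is a separate matter; 76.0% serves here only as the reference value.

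**2. Imbalance in stage with arm sizes fixed.** Let m of the 55 have dementia. With an exact 28/27 split and no strata, the number X in the arm of 28 is hypergeometric (55, m, 28). The table gives P(|X/28 − (m − X)/27| ≥ 0.20).

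| m (share) | X giving a gap of 20 points or more | Probability |
|---|---|---|
| 11 (20%) | ≤2 or ≥9 | 0.040 |
| 16 (29%) | ≤5 or ≥11 | 0.138 |
| 17 (31%) | ≤5 or ≥12 | 0.080 |
| 22 (40%) | ≤8 or ≥14 | 0.171 |
| 28 (51%) | ≤11 or ≥18 | 0.108 |

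The range is about 4% to 17%. It is not smooth, because one patient more or fewer moves the cut-off. Blocking alone does not remove this imbalance, since the arm sizes here are already as equal as possible.

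**3. Effect on the estimate.** The shift in the arm difference equals the imbalance in share times the stage difference D in mean change. With an imbalance of 0.20 and D of 1 to 3 points, it is 0.20 × 1 = 0.2 to 0.20 × 3 = 0.6 points, against the planned 10.

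**4. Effect on precision.** Fitting stage removes p(1 − p)D² from the variance, where p is the dementia share.
- D = 1, p = 0.2: 0.16 removed; SD √(169 − 0.16) = 12.99; power 76.0%.
- D = 3, p = 0.5: 2.25 removed; SD √(169 − 2.25) = 12.91; power 76.5%.

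The range of 76.0% to 76.5% is unchanged when the error degrees of freedom fall from 48 to 47 for the extra term.

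**5. Arm size.** Power is 76.0% at 25/25 and 74.3% at 20/30. Unequal arm size is therefore a minor issue.

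**The case against.** The strongest reply is that unstratified randomisation is valid: chance imbalance does not bias the comparison in expectation, and the test allows for it. That stands. The point concerns precision and credibility, not validity.

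Second, the analysed outcome is change, so a difference in MDRS level between MCI and dementia largely cancels within patients. That also stands, and it is why the effect is small. What remains is differential change by stage and regression to the mean. Adjusting for baseline MDRS would recover part of the same benefit.

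Third, Aim 3 repeatedly uses the MCI label, so the dementia share may be low. At 20%, the chance of a 20-point imbalance is only 4%. The admission criteria and the shared count of 55 nevertheless point to a mixed population.

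Some stronger readings are tempting but not supported:
- That the trial uses simple, unblocked randomisation. The protocol is silent, and naming the software does not reveal the method.
- That unblocked allocation is what puts 25 per arm at risk. Blocking does not secure it either: from an exact 28/27 split, five random drop-outs leave 25/25 only 33% of the time.
- That stage is the strongest baseline determinant of MDRS. No section says so.
- That imbalance would move the result by 1 to 2 points, and that adjustment would lift power to 77% to 82%. Both need a stage gap of 5 to 10 points in change, which is half to all of the planned treatment effect. Nothing in the documents supports a gap of that size.

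**Conclusion.** The point holds as a minor design improvement. The plan admits two cognitive stages, specifies no blocking or stratification, and names no stage term for Aim 3, although stage is known before allocation. A dementia imbalance of 20 percentage points or more would occur in roughly 4% to 17% of trials with a 28/27 split. Its likely consequence is modest: 0.2 to 0.6 MDRS points on the arm difference, and at most half a percentage point of power from adjustment, with larger effects only if stages differ by more than 3 points in change. These figures rest on an assumed dementia share of 20% to 50%, an assumed stage difference in change of 1 to 3 points, and an SD of 13 for the analysed measure. None of this means that the planned comparison is biased or invalid.

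**What to change.** Specify a concealed, pre-generated allocation list with randomly varying permuted blocks, stratified by MCI versus mild dementia. Blocks of 4 and 6 are a reasonable example. Blocks of 2 should be avoided, because the first assignment in each determines the second. Enter stage as a pre-specified term in the Aim 3 models for MDRS and for the MEG outcomes.

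The costs are slightly more administration, one degree of freedom per model, and some predictability if the staff who enrol also know past assignments. With blocks of 2 and 4, a simulation of guessing from the running balance predicted the next assignment correctly about 72% of the time, against 50% under simple randomisation. Larger varying blocks reduce this but do not remove it, so the list should be held by someone not involved in enrolment. The list can be changed only before randomisation begins; the model term can be added at any time before unblinding.

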AIM 1 Statistical Analysis and Sample Size: To address our primary research question, Spearman correlations will be used to identify frequency spectra small-worldness measures associated with the MDRS in eyes-closed data with a false detection rate set at 0.05 to handle the issue of multiple comparisons. We will then use linear regression to determine whether small-worldness in these specified frequency bands remain associated with the MDRS when controlling for each other as well as other important covariates, namely age and motor severity. A *sample size* of 45 (allowing for 5 drop-outs and/or unusable data-sets from the original 50) will allow us to detect correlations of 0.18 or higher between our MEG features and MDRS with 80% power 0.05 significance. This is comparable to correlations of 0.19 and higher seen in other resting state MEG studies of cognition.¹¹⁵ Planned secondary analyses will parallel our primary analysis to determine whether global efficiency, nodal efficiency or degree distribution are significantly associated with MDRS in linear regression models. Exploratory analyses will assess reactivity of these measures between eyes open and closed conditions and assess whether domain specific neuropsychological test scores are associated with connectivity within networks defined by domain related nodes (e.g. occipital nodes and visuospatial tests).

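### The Aim 1 power statement is wrong: with 45 subjects, power at a correlation of 0.18 is about 22%, not 80%, and the detectable correlation is about 0.40; the Exploratory Aim repeats the error

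*Combined protocol and SAP*

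**What the plan says.** Section IV.F, Aim 1, plans the primary analysis as follows: "Spearman correlations will be used to identify frequency spectra small-worldness measures associated with the MDRS in eyes-closed data". Multiplicity is to be controlled through the false discovery rate, at 0.05. Section IV.A (MEG Data Processing) defines six frequency bands, each analysed separately. Section IV.C (Aim 1) takes 25 subjects with mild cognitive impairment and 25 with normal cognition; Section IV.F allows for five losses, which leaves 45.

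The sample-size claim is that this number "will allow us to detect correlations of 0.18 or higher between our MEG features and MDRS with 80% power 0.05 significance". The plan then draws a comparison with earlier work: "This is comparable to correlations of 0.19 and higher seen in other resting state MEG studies of cognition". The plan does not say whether the test is one- or two-sided.

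For the Exploratory Aim, Section IV.F says: "Power considerations are similar as for Aim 1 with detection of correlations of 0.18 or higher between our MEG and MRI features". The power and significance level are the same as for Aim 1. It gives no sample size of its own, and Section IV.A makes the additional MRI sequences optional.

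**The concern.** A correlation of 0.18 explains about 3% of the variance (0.18² = 0.032). Detecting that reliably takes a few hundred subjects, so 45 looks far too few.

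The sentence is the only quantitative justification for the Aim 1 sample size. The comparison that follows tells the reader that the study can find effects at the lower end of those already reported. If that is untrue, a non-significant frequency band carries little information about correlations of that size. A reader who trusts the 80% could nevertheless take it as evidence against the network hypothesis. The Exploratory Aim carries the same risk.

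**Working it through.** **Inputs.** n = 45, r = 0.18, power 80%, significance 0.05, Spearman test and false discovery rate 0.05 (Section IV.F, Aim 1); six bands (Section IV.A); comparator r = 0.19 (Section IV.F, Aim 1). Two-sided testing is assumed, and one-sided is also shown.

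**Formulas.** Using the Fisher z-transform:

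- power = Φ(atanh(r)·√((n−3)/c) − z) plus a negligible opposite tail
- detectable r = tanh((z + 0.8416)/√((n−3)/c))
- required n = c·((z + 0.8416)/atanh(r))² + 3

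Here c = 1 for Pearson and 1.06 for Spearman, and z = 1.96 for two-sided 0.05.

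**Trying to reproduce the plan's figure.** atanh(0.18) = 0.1820 and √42 = 6.481, so the product is 1.179. Then Φ(1.179 − 1.96) = Φ(−0.781) = 0.218. The stated 80% is not reproduced; power is 21.8%. With the Spearman variance it is 20.9%. Simulation from bivariate normal data (100,000 datasets) gives 22.1% for Pearson and 20.1% for Spearman.

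**What 45 subjects can detect.** (1.96 + 0.8416)/6.481 = 0.432, and tanh(0.432) = 0.407. With the Spearman variance, √(42/1.06) = 6.295 and the result is 0.418. In simulation, Pearson reaches 79.3% at r = 0.40 and 80.4% at 0.405. Spearman reaches 79.7% at an underlying correlation of 0.425.

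**Sample size for r = 0.18.** (2.8016/0.1820)² + 3 = 240 for Pearson, or 255 with the Spearman variance.

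**Critical value.** With 43 degrees of freedom t = 2.017, so |r| must exceed 2.017/√(43 + 2.017²) = 0.294.

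**Other readings of the statement.**

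| Reading | Power at r = 0.18 | Detectable r at 80% |
|---|---|---|
| n = 45, two-sided | 21.8% | 0.407 |
| n = 45, one-sided | 32.1% | 0.366 |
| n = 50 (no losses), two-sided | 23.9% | 0.387 |
| n = 80 (25 + 55, all enrolled), two-sided | 35.9% | 0.309 |
| n = 45, two-sided 0.05/6, Pearson | 7.2% | 0.491 |
| n = 45, two-sided 0.05/6, Spearman variance | 6.8% | 0.503 |

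The first four rows use the Pearson variance. The 0.05/6 rows are the strictest step of a false discovery procedure over six bands.

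**At the comparator.** For r = 0.19 and n = 45, two-sided, power is 23.8% (22.8% with the Spearman variance).

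**A possible origin.** If 0.18 is Cohen's f² with one predictor and n = 45, the noncentral F distribution gives 79.4% power, close to the stated 80%. That f² corresponds to R² = 0.18/1.18 = 0.153, or |r| = 0.39. If 0.18 is R², then |r| = √0.18 = 0.424; Fisher z gives 83.5% power, and the simulated Spearman test at 0.425 gives 79.7%. The documents confirm neither reading.

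**The case against.** The strongest defence is that the number is mislabelled and the design is not at fault. On two squared scales, f² or R², 45 subjects do give close to 80% power. The published 0.19 might also be on a squared scale, in which case the comparison would be sound. Its citation is number 115, while the numbered reference list in the document ends at 42, so this cannot be checked. The plan also says 0.19 *and higher*, so 0.19 is the bottom of a range and not the expected effect.

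Part of this stands. The cause may well be a label, and the statement that the study would miss about three effects in four applies only to true correlations near 0.19. It does not rescue the text, which calls both figures correlations and compares them as such. A squared-scale reading itself implies a detectable correlation of 0.39 to 0.42.

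Other points have limited force.

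- Power under false discovery control depends on how many bands are truly associated, so 0.05/6 is a lower bound on sensitivity and not the expected case.
- The pooled sample is selected on cognition, so its correlation may exceed that in an unselected group. That bears on how large the true effect might be, not on power at 0.18.
- Section IV.E concedes that the sample is relatively small, but mainly in discussing the stimulation trial; it does not correct the Aim 1 figure.
- Aim 3 has its own sample-size calculation and is not affected.

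**Conclusion.** The statement is wrong as written and must be corrected. At n = 45 and two-sided 0.05, power at a correlation of 0.18 is about 22% (about 20% for Spearman), and the correlation detectable with 80% power is about 0.40 to 0.42, more than twice the stated value. At 0.19, the lower end of the cited range, the study would miss a true association about three times in four.

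The figures assume bivariate normal data and a two-sided test. A one-sided test leaves power at 32%, and none of the sample sizes in the table brings it near 80%. The Exploratory Aim carries the same error. Even if all 80 enrolled subjects accepted the optional sequences, the detectable correlation would be about 0.31 and power at 0.18 about 36%.

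**What to change.** In Section IV.F, Aim 1:

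- State that 45 evaluable subjects give 80% power (two-sided 0.05) for a correlation of about 0.40, or about 0.42 for the planned Spearman test, rising to about 0.5 at the strictest false discovery step over six bands. Give the power at 0.18 as about 22% (about 20% for Spearman).
- Name the effect-size scale, the test and the sidedness used.
- Remove or reverse the claim of comparability with 0.19. If the source proves to report squared values, convert both figures to correlations before comparing them.
- Add that a non-significant band does not rule out correlations below about 0.4.

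In the Exploratory Aim, replace 0.18 with the correlation detectable at the number of subjects expected to accept the optional scans, and state that number.

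The cost is wording only. No patients or procedures are added, but the stated detectable effect becomes less favourable.
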